#### **6.1.1. Participant Disposition**

A summary of the number of participants in each of the analysis set described will be provided (for primary analysis, Evaluable population will not be included). In addition, the number of participants enrolled by centre will be summarized by dose level using the "Enrolled" population. A summary of subject status and reason for study withdrawal will be provided. This display will show the number and percentage of participants who withdrew from the study, including primary reasons for study withdrawal. Reasons for study withdrawal will be presented in the order they are displayed in the eCRF.

A summary of study treatment status will be provided. This display will show the number and percentage of participants who are ongoing or discontinued study treatment and a summary of the primary reasons for discontinuation of study treatment. Reasons for study treatment discontinuation will be presented in the order they are displayed in the eCRF. A listing of study treatment discontinuation will be generated. The listing will include last dose date, and reasons for study treatment discontinuation. The 'Summary of Subject Status and Subject Disposition for the Study Conclusion Record' and the 'Summary of Treatment Status and Reasons for Discontinuation of Study Treatment' will be repeated, with the reason for withdrawal/discontinuation categorised as due to the COVID-19 pandemic, or non-due to the COVID-19 pandemic based on information collected on the COVID-19 Pandemic Study Impact form.

In this multicenter global study, enrolment will be presented by country and site.

Data from all participating centers will be integrated and no controlling for center-effect will be considered in the statistical analyses. It is anticipated that patient accrual will be spread thinly across centers and summaries of data by center is unlikely to be informative and will not be provided.

#### **6.1.2. Demographic and Baseline Characteristics**

The demographic characteristics (e.g., age, race, ethnicity, sex, baseline height, and baseline body weight and baseline BMI) will be summarized and listed. Age, height, weight and BMI will be summarized using the mean, standard deviation, minimum, median, and maximum. The count and percentage will be computed for sex and ethnicity.

Race and racial combinations will be summarized and listed.

Disease history and characteristics (e.g. time since initial diagnosis in years, stage at initial diagnosis, date of initial diagnosis) at initial diagnosis and screening will be listed. Separate summaries of disease characteristics at initial diagnosis and screening will be provided. Disease characteristics at screening, including stage, type of multiple myeloma, number of prior lines, and types of therapy, myeloma light chain and myeloma immunoglobulin, extramedullary disease, lytic bone lesion, and genetic characteristics (including high cytogenetic risk) will be summarized and listed.

Medical conditions collected at screening will be listed and will be summarized by past and current and by cancer-related and non-cancer related categories.

Substance use, including smoking history and alcohol use will be summarized.

Prior anti-cancer therapy will be coded using GSK Drug coding dictionary, then summarized by type of therapy and listed. A listing of prior anti-cancer therapy will show the relationship between ATC Level 1, Ingredient, and verbatim text. A summary of the best response to the most recent prior anti-cancer therapy will be provided. A summary of the number of prior anti-cancer therapy regimens will also be produced.

Prior anti-cancer therapy for multiple myeloma participants will also be summarized by type of therapy, and drug class. A summary of multiple myeloma participants' refractory to prior anti-cancer therapy by drug class will be provided.

Anti-cancer radiotherapy will be listed. Prior cancer and non-cancer related surgeries will be summarized. Prior and on treatment cancer and non-cancer related surgeries will be listed.

### **6.1.3. Protocol Deviations**

Important protocol deviations will be summarized.

Protocol deviations will be tracked by the study team throughout the conduct of the study. These protocol deviations will be reviewed to identify those considered as important as follows:

- Data will be reviewed prior to freezing the database to ensure all important deviations (where possible without knowing the study intervention details) are captured and categorised in the protocol deviations dataset.
- This dataset will be the basis for the summaries of important protocol deviations.

In addition to the overall summary of important protocol deviations, separate summaries will be produced for important protocol deviations related to COVID-19, and important protocol deviations not related to COVID-19 respectively.

### **6.1.4. Prior and Concomitant Medications**

Concomitant medications will be coded using both the GSK Drug and WHO Drug dictionaries. However, the summary will be based on GSK Drug dictionary only. The summary of concomitant medications will show the number and percentage of participants taking concomitant medications by Ingredient. Multi-ingredient products will

be summarized by their separate ingredients rather than as a combination of ingredients. Anatomical Therapeutic Chemical (ATC) classification Level 1 (Body System) information will be included in the dataset created but will not appear on the listing or summary.

In the summary of concomitant medications, each subject is counted once within each unique ingredient. For example, if a subject takes Amoxicillin on two separate occasions, the subject is counted only once under the ingredient “Amoxicillin”. In the summary of concomitant medications, the ingredients will be summarized by the base only, using CMBASECD and CMBASE. Note: In order to be considered a concomitant medication, the concomitant medication must have been taken at some point during the on-treatment window.

Prophylactic medication for infusion-related reactions and prophylactic topical eye medications will be summarized by drug class and drug name and listed separately.

Blood products or blood supportive care products with onset date within the on-treatment window will be included in the summary tables. The frequency and percentage of participants using blood products and blood supportive care products after the start of study medication will be provided. Supporting listings will also be provided.

#### **6.1.5. Subsequent Anti-Cancer Therapies**

The number and percentage of participants that received chemotherapy, immunotherapy, hormonal therapy, biologic therapy, radioactive therapy, small molecule targeted therapy, as subsequent anti-cancer therapy will be summarized. Time from study treatment discontinuation to the first post study treatment anti-cancer therapy will also be included in this summary table, if available.

Follow-up anti-cancer therapy will be coded using GSK Drug coding dictionary, then summarized by ingredient. A listing of the type of follow-up anti-cancer therapy received (chemotherapy, immunotherapy, hormonal therapy, biologic therapy, radioactive therapy, and small molecule targeted therapy) for each subject will be provided.

#### **6.1.6. Additional Analyses Due to the COVID-19 Pandemic**

A participant is defined as having a suspected, probable or confirmed COVID-19 infection during the study if the answer is “Confirmed”, “Probable” or “Suspected” to the case diagnosis question from the COVID-19 coronavirus infection assessment eCRF.

Summaries and listings of the numbers of participants with a suspected, probable or confirmed COVID-19 infection, and of COVID-19 test results will be based on GSK Core Data Standards.

## 6.2. Appendix 2 Data Derivations Rule

### 6.2.1. Criteria for Potential Clinical Importance

#### 6.2.1.1. Laboratory Values

Reference ranges for all laboratory parameters collected throughout the study are provided by the laboratory. A laboratory value that is outside the reference range is considered either high abnormal (value above the upper limit of the reference range) or low abnormal (value below the lower limit of the reference range). Note: a high abnormal or low abnormal laboratory value is not necessarily of clinical concern. The laboratory reference ranges will be provided on the listings of laboratory data. Clinical laboratory test results outside of the reference range will be flagged in the listings.

To identify laboratory values of potential clinical importance, National Cancer Institute Common Terminology Criteria for Adverse Events (NCI-CTCAE v5.0) will be used to assign grades to the relevant laboratory parameters. NCI-CTCAE v5.0 can be found at <http://ctep.cancer.gov/reporting/ctc.html>.

For laboratory data which are not listed in the NCI CTCAE v5.0, a summary of values outside the normal range will be provided.

#### 6.2.1.2. ECG Parameters and vital signs

For ECG and vital signs, outputs per the most updated IDSL standard up to the SAP effective date will be provided.

Unless otherwise specified, ECG displays will be based on central reading.

### 6.2.2. Study Period

Assessments and events will be classified according to the date/time of occurrence relative to date/time of first dose of study treatment.

Study Phase	Definition
Pre-Treatment	Date/time $\leq$ Study Treatment Start Date/time
On-Treatment	Study Treatment Start Date/time < Date/time $\leq$ Last Dose Date + 70 days
Post-Treatment	Date/time > Study Treatment Stop Date + 70 days

For assessment or event on the first dosing day, whether it is Pre-Treatment or On-Treatment should be based on time if available. If time is not available, the first dosing day (Day 1) is considered Pre-Treatment for ECOG, ECG, vital signs, liver events, lab tests, cardiac scan, and other safety domains, and On-Treatment for adverse events and concomitant medications.

Concomitant Medication and Blood and Blood Supportive Care Product start and end dates will be assigned to study time periods in relation to first dose of study treatment as defined below. The start date references time flag variables and end date reference time flag variables will be added to the concomitant medications and blood and blood supportive products datasets, respectively.

- Start relative to treatment: Assign to 'BEFORE' if start date is prior to study treatment start date or if subject has not taken any study treatment or (start date is missing and end date is before study treatment start date). Else assign to 'DURING' if the start date falls into the on-treatment period as defined above or if subject is ongoing (not all study treatment discontinuation records completed) or start date is missing. Else assign to 'AFTER' if start date is after the on-treatment period.
- End relative to treatment: Assign to 'BEFORE' if end date is prior to study treatment start date or if subject has not taken any study treatment. Else assign to 'DURING' if start date falls into the on-treatment period or if subject is ongoing (not all study treatment discontinuation records completed) or (end date is missing and start relative to treatment not 'AFTER'). Else assign to 'AFTER' if start date is after the on-treatment period or (end date is missing and start relative to treatment='AFTER').

Only on-treatment blood and blood supportive care products that start after the start of study treatment are included in the Blood Products and Blood Supportive Care Product summaries. Therefore, for summary tables, include blood and blood supportive care product records where start relative to treatment in ('DURING') and end relative to treatment in ('DURING','AFTER'). All data will be reported in listings.

Concomitant medication starts relative to treatment and end relative to treatment flags are used to select data to include in the Concomitant Medication summaries as follows:

- Summary of Concomitant Medications: This summary will contain medications including those with start date prior to study treatment start date and continue (missing end date or end date after study treatment start date) on therapy. Note that any medications with start date and end date prior to study treatment start date will be excluded. In addition, any medication that was started during post-therapy will be excluded. Include concomitant medication records where start relative to treatment in ('BEFORE','DURING') and end relative to treatment in ('DURING','AFTER').
- Summary of Concomitant Medications with On-Therapy Onset: This summary will contain medications with start date after study treatment start date. In addition, any medication that was started during post-therapy (see above for definition of posttherapy) will be excluded. Include concomitant medication records where start relative to treatment in ('DURING') and end relative to treatment in ('DURING','AFTER').

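### SAP 6.2.2: the end-relative-to-treatment flag tests the start date, so in discontinued participants medications begun before first dose and stopped later drop out of the concomitant medication summary

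*SAP*

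**What the plan says.** SAP 6.2.2 (Study Period) sets two flags for each concomitant medication and each blood or blood supportive care product.

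- **Start flag.** "Start relative to treatment: Assign to 'BEFORE' if start date is prior to study treatment start date" is the first condition. A start in the on-treatment period gives DURING, as does an ongoing participant or a missing start date. A start after that period gives AFTER.
- **End flag, BEFORE.** The condition reads: "End relative to treatment: Assign to 'BEFORE' if end date is prior to study treatment start date or if subject has not taken any study" (the quote stops one word short of the sentence end). This tests the end date.
- **End flag, DURING.** It is given "if start date falls into the on-treatment period or if subject is ongoing", where ongoing means that the discontinuation records are not yet complete. This tests the start date. A third route covers records where "end date is missing and start relative to treatment not 'AFTER".
- **End flag, AFTER.** The condition reads: "Else assign to 'AFTER' if start date is after the on-treatment period or (end date is missing and start relative to treatment='AFTER"). This tests the start date again.

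The rule has no default branch.

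The same section then filters on the flags. The Summary of Concomitant Medications takes start flag BEFORE or DURING together with end flag DURING or AFTER. The on-therapy-onset and blood-product summaries take start flag DURING with the same end flags.

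The prose gives the intended content of the main summary: "This summary will contain medications including those with start date prior to study treatment start date and continue", where continuing means a missing end date or one later than treatment start. SAP 6.1.4 (Prior and Concomitant Medications) defines the class: "the concomitant medication must have been taken at some point during the on-treatment window".

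**The concern.** The end flag is meant to say when a medication stopped, yet two of its three values are decided mainly by when it started. A drug taken before first dose and stopped during or after treatment is an ordinary kind of concomitant medication, and it is the kind for which start date and end date fall in different periods. If it gets no end flag, the filter removes it and the table contradicts its own description in the same section.

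The outcome also depends on something unrelated to the medication. While the participant is ongoing, the ongoing clause assigns DURING and the record is kept. Once the discontinuation records are complete, the same record disappears. Counts for this class could therefore fall between two data cuts with no change in the medication data.

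**Working it through.** The plan gives no figure to reproduce. The check applies the flag rules and the filter literally and compares the result with the prose of 6.2.2.

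**One record traced.** The participant received study treatment and has discontinued. The medication starts on day -30 and ends on day 50, inside the on-treatment period.

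1. Start flag: the start precedes first dose, so BEFORE.
2. End flag BEFORE? No. Day 50 is not before first dose.
3. End flag DURING? No. The start date is not on-treatment, the participant is not ongoing, and the end date is not missing.
4. End flag AFTER? No. The start date is not after the on-treatment period, and the end date is not missing.
5. The end flag stays unassigned, so the filter excludes the record. By the prose of 6.2.2 it belongs in the summary.

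**All patterns, discontinued participant.** Each date may be before first dose (pre), on-treatment (on), post-treatment (post) or missing; patterns with the end before the start are impossible. As 6.2.2 provides for concomitant medications when no time is recorded, Day 1 counts as on-treatment.

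| Start | End | Start flag | End flag as written | In summary as written | Should be in | End flag if end date is tested |
|---|---|---|---|---|---|---|
| pre | pre | BEFORE | BEFORE | no | no | BEFORE |
| pre | on | BEFORE | **none** | **no** | **yes** | DURING |
| pre | post | BEFORE | **none** | **no** | **yes** | AFTER |
| pre | missing | BEFORE | DURING | yes | yes | DURING |
| on | on | DURING | DURING | yes | yes | DURING |
| on | post | DURING | DURING | yes | yes | AFTER |
| on | missing | DURING | DURING | yes | yes | DURING |
| post | post | AFTER | AFTER | no | no | AFTER |
| post | missing | AFTER | AFTER | no | no | AFTER |
| missing | pre | BEFORE | BEFORE | no | no | BEFORE |
| missing | on | DURING | **none** | **no** | **yes** | DURING |
| missing | post | DURING | **none** | **no** | **yes** | AFTER |
| missing | missing | DURING | DURING | yes | yes | DURING |

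Four of 13 patterns are wrongly lost. For the two with a missing start, the prose does not mention missing start dates. They are counted as due for inclusion because the start rule itself places them in DURING and neither exclusion in the prose applies. With start flag DURING they also meet the start condition of the on-therapy-onset and blood-product filters, and they fail those only for want of an end flag.

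**Ongoing participant.** No date is post-treatment, which leaves 8 patterns. None is wrongly lost, because the ongoing clause assigns DURING whenever the end date is not before first dose.

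**After correction.** With the end date in both clauses, all 13 + 8 = 21 patterns receive an end flag and agree with the expected inclusion.

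**Internal sign of a slip.** As written, a treated participant's record can reach end flag AFTER only if the start is post-treatment or the start flag is already AFTER. Ongoing participants have been assigned DURING by then. Every record with end flag AFTER therefore has start flag AFTER, which all three filters exclude, so the AFTER in the filters' end condition can never select anything. It has a purpose only if the end flag tests the end date.

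**The case against.** **The intent is plain.** The prose of 6.2.2 and the definition in 6.1.4 say what belongs in the table, SAP section 1 sends further data handling to the Output and Programming Specification, and section 6.1 bases these displays on the sponsor's core data standards. A programmer may well implement the right rule. That stands as a limit: the loss follows from the literal text and is not an established result. It does not excuse the text, since neither source is shown and the SAP states an explicit algorithm that contradicts its own prose.

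**The table may change less than the record count.** Section 6.1.4 counts each participant once per ingredient, so a lost record matters only if no other qualifying record of that ingredient exists. Records with no end date are kept. Section 6.2.7 imputes partial start dates for medications, so if imputed dates are used for assigning periods, only completely missing start dates reach the missing-start branch. All of this stands.

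**Between-arm distortion.** A reader might infer that the arm that stops treatment sooner is under-counted more, and take the planned median PFS of 4 versus 7 months (section 5.2) as evidence that this is pom/dex. The SAP does not support that. It gives no discontinuation rates, and treatment also ends for toxicity, withdrawal or death. As an illustration only, take PFS as time on treatment, exponential, with uniform accrual over 20 months and a cut-off at 25 months. The share off treatment is 1 - (exp(-5λ) - exp(-25λ))/(20λ), with λ = ln 2/median:

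- Median 4: λ = 0.1733; 1 - (0.4204 - 0.0131)/3.466 = about 88%.
- Median 7: λ = 0.0990; 1 - (0.6095 - 0.0841)/1.980 = about 73%.

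Most of both arms would be exposed to the rule. By 60 months both shares exceed 99%. Direction is open as well, because a longer on-treatment period leaves more time for a pre-existing drug to be stopped, which could put more affected records in the longer-treated arm. Nor does the SAP plan any test or estimate comparing concomitant medication between arms.

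**Conclusion.** The point holds as an error in a stated derivation rule. Applied literally to participants whose discontinuation records are complete, it leaves 4 of 13 start/end patterns without an end flag: start before first dose or completely missing, with a known end date on- or post-treatment. The first two are lost from the Summary of Concomitant Medications. The missing-start patterns are lost from that summary and from the on-therapy-onset and blood-product summaries. Records with a known on-treatment start are unaffected in all three; at most they carry DURING where AFTER would be correct, which does not alter inclusion.

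The number of records or participants involved cannot be stated, because it depends on data the SAP does not contain. Inclusion does depend on treatment status at the data cut-off, but the size and direction of any difference between arms cannot be determined. The effect is confined to descriptive summaries. Listings report all data, and no efficacy analysis uses these flags.

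The conclusion rests on three assumptions: the rule is programmed as written, the participant received study treatment, and Day 1 counts as on-treatment for medications. The correction is worth making because the rule as written yields a wrong table and costs almost nothing to repair.

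**What to change.** In the end-relative-to-treatment bullet of SAP 6.2.2, replace the start date by the end date in the DURING and AFTER clauses:

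- **DURING** if the end date falls in the on-treatment period, or the participant is ongoing, or the end date is missing and the start flag is not AFTER.
- **AFTER** if the end date is after the on-treatment period, or the end date is missing and the start flag is AFTER.

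Leave the BEFORE clause, the start-flag rule and the three inclusion filters as they are. The cost is a wording correction in two places and a programming check. Running the 21 patterns above through the code would serve as that check.

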### 6.2.3. Treatment Emergent Flag for Adverse Events

Flag	Definition
Treatment Emergent	
 
• Study Treatment Start Date ≤ AE Start Date ≤ min(Study Treatment Stop Date + 70 day, Start of anti-cancer therapy)
 
• AE Start Date is missing
 

All AE displays will use the “treatment emergent” definition. One additional AE display by preferred term may be generated for the AEs between the start of anti-cancer therapy and Study Treatment Stop Date + 70 day if a subject starts an anti-cancer therapy before the Study Treatment Stop Date + 70 day.

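### The treatment-emergent flag in Section 6.2.3 is not reconciled with Section 6.2.2 in two narrow cases: AEs timed before the first dose on Day 1, and anti-cancer therapy recorded while study drug is still being given

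*SAP*

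**What the plan says.** Two adjacent sections of the SAP's Appendix 2 place an AE relative to study treatment.

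- **Section 6.2.2 (Study Period)** works on date and time: "Assessments and events will be classified according to the date/time of occurrence relative to date/time of first dose of study treatment". For the first dosing day it adds: "For assessment or event on the first dosing day, whether it is Pre-Treatment or On-Treatment should be based on time if available". Where no time exists, Day 1 counts as Pre-Treatment for most safety domains "and On-Treatment for adverse events and concomitant medications". The On-Treatment period ends at "Last Dose Date + 70 days", with no cut at anti-cancer therapy.
- **Section 6.2.3 (Treatment Emergent Flag)** works on dates only. The condition is "Study Treatment Start Date ≤ AE Start Date ≤ min(Study Treatment Stop Date + 70 day, Start of anti-cancer therapy"; an AE with a missing start date is also flagged. On reach it says: "All AE displays will use the “treatment emergent” definition". One further table by preferred term is optional, for AEs between the start of anti-cancer therapy and 70 days after the stop date.

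Section 6.2.3 does not say which therapies count as anti-cancer therapy, or whether the therapy must start after the last dose. The only restriction of the term, in Section 4.3.2.1, limits it to new systemic drugs and leaves out radiotherapy and surgery, but only for the ORR and CBR analyses.

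**The concern.** The flag decides which events enter the AE, SAE, AESI and related-event tables, so its limits should agree with the study periods defined one section earlier.

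At the lower limit, a date comparison overrides the time rule. An event known to have begun before any drug was given can be counted as treatment-emergent.

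At the upper limit, the minimum can fall before the stop date. If that happens, AEs that occur while the participant is still receiving study drug are not treatment-emergent. They could then appear only in a table that need not be produced and for which no grade, seriousness or relatedness is specified. Because the trigger is undefined, two programmers could also reach different tables, for example on whether palliative radiotherapy closes the window.

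**Working it through.** No figure in the plan is at issue, so the check applies both rules to the same test events. The SAP gives no individual dates. The following are assumptions for illustration: first dose at 12:00 on Day 1, and last dose on day 210, taken as the stop date. Two therapy dates are tried: day 63 (during dosing) and day 240 (after it).

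Rules applied:
- 6.2.2: on Day 1, a timed AE is Pre-Treatment if its time is at or before the dose and On-Treatment if later; an untimed AE is On-Treatment. After Day 1, an AE is On-Treatment up to last dose + 70 days.
- 6.2.3: treatment-emergent if start date ≤ AE date ≤ min(stop + 70, therapy start).

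| Test AE | 6.2.2 | 6.2.3 | Result |
|---|---|---|---|
| Day 1, timed 08:00, before dose | Pre-Treatment | Emergent | Conflict |
| Day 1, timed after dose | On-Treatment | Emergent | Agree |
| Day 1, no time | On-Treatment | Emergent | Agree |
| Day 100, therapy day 63, still dosing | On-Treatment | Not emergent | Conflict |
| Day 250, therapy day 240, dosing ended | On-Treatment | Not emergent | Intended cut after treatment |

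Size of the second conflict in this example:
- Limit without therapy: 210 + 70 = day 280.
- Limit under 6.2.3: min(280, 63) = day 63.
- Window lost: 280 − 63 = 217 days, of which 210 − 63 = 147 are during dosing and 217 − 147 = 70 follow the last dose.

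With the limit min(stop + 70, max(stop, therapy start)):
- Therapy on day 63: min(280, max(210, 63)) = day 210. The day 100 AE becomes emergent and the 147 on-drug days return.
- Therapy on day 240: min(280, max(210, 240)) = day 240. The day 250 AE stays out.
- No therapy: the limit stays at day 280.

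The revised limit therefore changes the flag only when therapy starts before the stop date.

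**The case against.** The strongest reply is that neither case may arise often.

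**Lower limit.** The SAP does not say that AE times are collected generally. The hour-level reporting is for infusion-related reactions (Section 4.5.2.1), and those identified from the term list count only after the infusion has started, so they cannot be pre-dose. A date rule also errs towards counting events. And a pre-dose event reaches a related-AE table only if the investigator judged it related or relatedness is missing. All of this stands; it makes the conflict small but does not remove it.

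**Upper limit.** Section 6.1.5 speaks of subsequent and follow-up therapy, timed from study treatment discontinuation. Section 6.2.7 moves a partial therapy date in the month of last dose to the day after that dose or the month end. Both presume therapy after the last dose, where the missing floor has no effect. Whether therapy can overlap with dosing is a protocol matter, and the protocol is not at hand. Ending the window at new therapy is also a legitimate way to avoid charging later-therapy events to study drug. This stands too, and if a start after the last dose is what is meant, 6.2.3 should say so.

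**A stronger reading.** A reader might take Section 6.1.2, "Prior and on treatment cancer and non-cancer related surgeries will be listed", as proof that anti-cancer procedures occur during dosing and close the window. It is not proof. On-Treatment runs to 70 days after the last dose, so such surgery may follow the last dose, and nothing in 6.2.3 says that surgery counts as anti-cancer therapy.

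The separate treatment-emergent table in Section 4.5.2 might suggest that the other AE tables are unrestricted, but 6.2.3 states that all AE displays use the flag. Deaths (Section 4.5.2.2) and laboratory grade shifts (Section 4.5.4.1) are specified separately and are not stated to depend on it.

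**Conclusion.** The point holds as a failure to reconcile two sections in edge cases. Read literally, 6.2.3 counts a Day 1 AE timed at or before the first dose that 6.2.2 calls Pre-Treatment. It also drops on-drug AEs that 6.2.2 calls On-Treatment if a qualifying therapy is recorded before the stop date, for example as a protocol deviation, or as radiotherapy if that counts.

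The effect is probably small at both limits. How many participants are affected cannot be taken from the document: it depends on whether AE times are recorded, on what counts as anti-cancer therapy, and on how often such therapy overlaps with dosing. The 147 on-drug days describe one assumed participant and are not an estimate for the trial. A reader might infer that the flag is wrong at both ends as a rule, or that the main safety tables are materially distorted. The SAP does not support either inference: untimed Day 1 AEs agree in both sections, and the cut at new therapy after treatment ends is a stated and defensible choice.

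**What to change.** Amend Section 6.2.3 in three places:

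1. On Day 1, compare the AE start date and time with the first-dose date and time when both times are recorded; otherwise keep the present date rule.
2. Set the upper limit to min(Stop Date + 70 days, max(Stop Date, start of new anti-cancer therapy)), and to Stop Date + 70 days when no such therapy is recorded. The optional preferred-term table should then begin at the new cut.
3. State whether anti-cancer therapy means new systemic drugs only, as in the ORR and CBR rule, or also includes radiotherapy and surgery.

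The cost is a few clauses of SAP text and a small change to the AE flag program. No new data are needed, and the cut at new therapy after study treatment stops is unchanged.
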